### **Archival Tumor Collection**

If available, and with the patient's consent, archival tissue specimens should be submitted for molecular correlative studies. Archival tumor block (formalin-fixed paraffin-embedded) from initial breast diagnosis, or other specimen obtained prior to study, should be submitted, along with the corresponding path report, within four weeks of patient registration. If tissue blocks cannot be sent, 8-12 unstained slides may be submitted instead.

Fixed tissues, including paraffin-embedded tumor blocks or formalin-fixed tissues should be sent at ambient temperature. Do not send in the same box as the frozen plasma. Formalin fixed cells should be placed in a sealable bag with absorbent material and placed in an appropriate box or container for the shipping of a potentially hazardous material.

Address shipments to:

Analytical Pharma. Lab  
City of Hope

[name]  
[name]  
[name]  
[contact], [name]  
Email: [[contact]](mailto:[contact])

We anticipate access to formalin fixed paraffin embedded (FFPE) primary tumor tissue specimens for approximately 62 patients of the total 71 possible accrued to the clinical trial. Depending on the specific *BRCA* mutation, we will use IHC to assess *BRCA* protein expression in baseline tumors. We do not expect to identify pre-treatment reversion or resistance since one of the near obligatory steps in development of *BRCA*-associated cancer is the somatic or acquired loss of the wt allele. Subsequent genetic instability could generate reversion mutations in a small subfraction of the samples, but these subfractions are unlikely to be detectable unless subjected to selective pressure.

All specimens shipped must be accompanied by the Specimen Submission form found in Appendix D. Additionally, a copy of that completed form must be faxed to the Data Coordinating Center at City of Hope, [contact] when specimens are shipped.

The Federal guidelines for shipment are as follows:

- a. The specimen must be wrapped in an absorbable material;
- b. The specimen must then be placed in an AIRTIGHT container (like a resealable bag);
- c. Pack the resealable bag and specimen in a styrofoam shipping container;
- d. Pack the styrofoam shipping container in a cardboard box.
- e. The cardboard box must be marked as "BIOHAZARD."

## 11 STUDY CALENDAR

Baseline evaluations are to be conducted within 7 days prior to start of protocol therapy. Scans and x-rays must be done within 28 days prior to the start of therapy. In the event that the patient's condition is deteriorating, laboratory evaluations should be repeated within 48 hours prior to initiation of the next cycle of therapy. Tests indicated for the following weeks may be performed within  $\pm$  2 days of the indicated dates. Subsequent cycles can be adjusted  $\pm$  48 hours.

If a patient has been on a steady dose of ABT-888 as a single agent for at least 9 months, she/he can reduce visits at the enrolling institution to every 24 weeks, provided that he/she is seen by the local/primary MD with labs (and labs/notes sent to the center), every 3 weeks.

	Pre-Study	Cycle 1			Cycle 2			Cycle 3			Subsequent Cycles			Off Study e
		Wk 1	Wk 2	Wk 3	Wk 4	Wk 5	Wk 6	Wk 7	Wk 8	Wk 9	Wk 10	Wk 11	Wk 12	
ABT-888		X	X	X	X	X	X	X	X	X	X	X	X	
Carboplatin*		X			X			X			X			
Informed consent	X													
Demographics	X													
Medical history	X													
Concurrent meds	X	X-----									X			
Physical exam	X	X			X			X			X			X
Vital signs	X	X			X			X			X			X
Height	X													
Weight	X	X			X			X			X			X
Performance Status	X	X			X			X			X			X
CBC w/diff, plts a	X	X	X	X	X	X	X	X	X	X	X	X	X	X
Serum chemistry a,b	X	X	X	X	X	X	X	X	X	X	X	X	X	X
Urinalysis	X													
EKG (as indicated and needed)	X													

		Cycle 1			Cycle 2			Cycle 3			Subsequent Cycles			
	Pre-Study	Wk 1	Wk 2	Wk 3	Wk 4	Wk 5	Wk 6	Wk 7	Wk 8	Wk 9	Wk 10	Wk 11	Wk 12	Off Study e
Adverse event evaluation		X-----X												X
Tumor measurements	X	Tumor measurements are to be done at the end of cycle 3 and then repeat every 3 cycles. Documentation (radiologic) must be provided for patients removed from study for progressive disease.												X e
Radiologic evaluation g	X	1st scan will be done at the end of cycle 3 All subsequent scans will be done every 3 cycles of therapy. If the subject has a complete response/no evidence of disease or stable findings for more than a year, then annual evaluation is acceptable unless newly symptomatic.												X e
Urine or Serum Pregnancy Test	X c													
Tumor Biopsy d	X				X									X e
Pharmacodynamic blood draw f	X	X			X									
Archival Tumor Tissue	X													

a: If no greater than Grade 1 toxicities were seen on the most recent CBC and Serum Chemistry lab tests, after 2 cycles on a dose level, weekly CBC and Serum Chemistry will become optional (option to reduce to once per cycle).  
b: Albumin, alkaline phosphatase, total bilirubin, bicarbonate, BUN, calcium, chloride, creatinine, glucose, potassium, total protein, SGOT [AST], SGPT [ALT], sodium. Phosphorous at pre-study only.  
c: Serum or urine pregnancy test (women of childbearing potential)  
d: Optional  
e: Off-study evaluation  
f: Described in section 9.2. For Phase II patients, PD draws are also required on Cycle X and Cycle X+1. For Phase I patients, discontinue correlative blood draws for all cases beyond cycle 2.  
g. Patients that have been on treatment for more than 2 years may have their radiologic evaluations every 4 cycles (12 weeks).  
\* For patients receiving carboplatin either as part of the lead-in, or in the phase II part of the trial, after progression on ABT-888 alone

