## 6 DOSING DELAYS/DOSE MODIFICATIONS

Patients should meet the laboratory parameters outlined in section 3.1.8 and the performance status in section 3.1.6 before initiation of each cycle of therapy. All toxicities (except alopecia and lymphopenia, hyperglycemia, hypoalbuminemia, elevated serum alkaline phosphatase, WBC, and hemoglobin) should have resolved to grade 1 or lesser severity before initiation of the next cycle of therapy.

Qualifying laboratory tests can be obtained up to 72 hours before planned initiation of therapy from the third cycle onwards.

Dose adjustments are to be made according to the organ system showing the greatest degree of toxicity. The descriptions and grading scales found in the revised NCI Common Terminology Criteria for Adverse Events (CTCAE) version 5.0 will be utilized for AE reporting beginning April 1, 2018. All appropriate treatment areas should have access to a copy of the CTCAE version 5.0. A copy of the CTCAE version 5.0 can be downloaded from the CTEP web site [http://ctep.cancer.gov/protocolDevelopment/electronic\\_applications/ctc.htm](http://ctep.cancer.gov/protocolDevelopment/electronic_applications/ctc.htm).

The dose levels and the general approach to dose modification of ABT-888 therapy is shown in Table 4. Specific dose modification information for some AEs are provided in other sections. AEs should be treated with the appropriate maximum supportive care, and dose reductions should be clearly documented in the electronic case report form (eCRF).

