## 14 STATISTICAL CONSIDERATIONS

### 14.1 STUDY DESIGN/ENDPOINTS

The design of this Phase II trial is also described in Section 5.0.

All patients who begin treatment as part of this trial will be accounted for in the summary of results, and the outcome status (in terms of toxicity, response, reason off study, progression, and survival) will be reported.

The toxicities observed will be summarized in terms of type (organ affected or laboratory determination such as absolute neutrophil count), severity (by CTCAE and nadir or maximum values for the laboratory measures), time of onset (i.e. course number), duration, and reversibility or outcome. Tables will be created to summarize these toxicities and side effects by course.

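### Blood tests may drop from weekly to once per cycle after two cycles on a dose level, yet Section 14.1 tabulates laboratory toxicity by course with no allowance for the change, so later courses can be under-recorded

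*Combined protocol and SAP*

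**What the plan says.** The Section 11 calendar marks CBC and serum chemistry every week, in later cycles as well as early ones. Footnote a adds an option with two conditions, one on the latest result only and one on time: "If no greater than Grade 1 toxicities were seen on the most recent CBC and Serum Chemistry lab tests, after 2 cycles". The count of cycles is per dose level. Once both conditions hold, the weekly draws are no longer mandatory and one per cycle suffices.

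Section 6 governs the start of every cycle. "Patients should meet the laboratory parameters outlined in section 3.1.8" (ANC, platelets, bilirubin, transaminases, creatinine), and "All toxicities (except alopecia and lymphopenia, hyperglycemia, hypoalbuminemia, elevated serum alkaline phosphatase, WBC, and hemoglobin) should have resolved to grade 1 or lesser severity". On timing it says: "Qualifying laboratory tests can be obtained up to 72 hours before planned initiation of therapy from the third cycle onwards".

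Section 14.1 describes the safety summary. Severity is given by CTCAE grade and by "nadir or maximum values for the laboratory measures", onset is given by course number, and "Tables will be created to summarize these toxicities and side effects by course". It gives no denominator of draws, no restriction to courses sampled alike, and no caveat about the schedule change.

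**The concern.** A recorded nadir is the lowest value among the samples taken, and a recorded worst grade is the highest among them. Both depend on how many samples there are. If courses 1 and 2 have three draws each and many later courses have one, a by-course table mixes a change in patients' blood counts with a change in how often they were measured.

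Two readings are at risk. A lower grade 3-4 rate after course 2 could be taken as improving tolerance. The contrast between single-agent ABT-888 and the combination could also be distorted. Footnote a counts cycles on a dose level, so on a literal reading weekly draws restart when a patient moves to carboplatin plus ABT-888, while long single-agent exposure may be thinly sampled. Safety and tolerability of both regimens is a secondary objective (Section 1.2), and Section 6.1 calls neutropenia and thrombocytopenia common reactions to ABT-888.

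**Working it through.** The plan states no figure on this point, so there is none to reproduce. The check compares the rules and then illustrates the size.

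**1. Draws per cycle.** Weekly sampling of a 21-day cycle gives 3 draws; the option gives 1. The reduction is (3 - 1)/3 = 67%.

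**2. Which draw remains.** Section 6 requires qualifying laboratory values before every cycle, so a patient with one draw per cycle will naturally have that one. It is taken when values have recovered enough to treat. Section 11 also lets patients on a steady single-agent dose for at least 9 months have local laboratory tests every 3 weeks, which is again one draw per cycle.

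**3. Who can use the option.** For ANC, platelets and most chemistry, the values that clear a patient to start a cycle largely satisfy footnote a too. Two limits apply.
- Section 6 exempts lymphocytes, WBC, hemoglobin, glucose, albumin and alkaline phosphatase. Footnote a exempts nothing, so a patient above grade 1 on one of these may start a cycle and still owe weekly draws.
- Table 5 calls for an ABT-888 dose reduction after a grade 3-4 ANC or platelet value, and Table 6 after hemoglobin below 8 g/dL. The patient is then on a new dose level and the two-cycle count restarts.

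The thinner schedule therefore falls mainly on patients without a recent detected grade 3-4 ANC or platelet event. Cycle 3 is the earliest it can start.

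**4. Safeguards.** Section 6.1 requires at least weekly counts while ABT-888 is held, but only once a toxicity has been found. Section 11 asks for repeat tests in a deteriorating patient within 48 hours before the next cycle, which is again a pre-cycle test.

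**5. Size at constant true risk.** All inputs here are assumptions: the chance p that a given test shows grade 3-4, and the week-to-week correlation ρ of a latent normal value. With X₁ ~ N(0,1) and Xⱼ = ρXⱼ₋₁ + √(1 - ρ²)·εⱼ, a test is grade 3-4 if Xⱼ exceeds the normal quantile at 1 - p. The weekly rate is P(at least one of three tests is grade 3-4) and the once-per-cycle rate is p. At ρ = 0 this has a closed form: for p = 0.05 the weekly rate is 1 - 0.95³ = 0.143. Simulation with 400,000 patient-cycles per cell gave:

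| p | ρ | 3 tests | 1 test | ratio |
|---|---|---|---|---|
| 0.02 | 0 | 0.059 | 0.020 | 0.34 |
| 0.02 | 0.95 | 0.031 | 0.020 | 0.64 |
| 0.05 | 0 | 0.142 | 0.049 | 0.35 |
| 0.05 | 0.5 | 0.123 | 0.050 | 0.41 |
| 0.05 | 0.95 | 0.073 | 0.050 | 0.69 |
| 0.10 | 0 | 0.271 | 0.101 | 0.37 |
| 0.10 | 0.95 | 0.139 | 0.100 | 0.72 |

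The ratio runs from 0.34 to 0.72.

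**6. Partial uptake.** If half the patients use the option, the recorded rate relative to weekly testing is (1 + ratio)/2: (1 + 0.34)/2 = 0.67 and (1 + 0.72)/2 = 0.86.

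**7. Limiting case.** Suppose every non-exempt event starts and recovers between pre-cycle tests and weekly draws would find them all. With true rate q and uptake f, the recorded rate is q(1 - f). For q = 20% this is 10% at f = 0.5 and 0% at f = 1. This is a bound that follows from the assumed pattern, not an estimate.

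**The case against.** The strongest reply is that no planned inference is harmed. Section 14.1 plans descriptive tables with no trend test, and Section 14.4 treats work on observed toxicities as exploratory. The primary response endpoint uses no blood counts. The calendar default stays weekly, and the option may have been little used. Section 6 records that by 8/6/18 the study was closed to accrual, with three patients left, all on single-agent ABT-888. This stands as a limit on importance. It does not remove the problem, because a descriptive table is still read across its columns and these columns can rest on different numbers of draws.

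Several stronger readings are tempting, and the documents do not support them.
- **Laboratory toxicity must fall from cycle 3.** The reduction is optional, uptake is unknown, the count is per dose level, and a real rise in cumulative toxicity could offset the loss.
- **A patient with a grade 4 neutrophil or platelet nadir in cycle 2 who recovers in time moves to thin sampling in cycle 3.** If that nadir is detected, Table 5 leads to a dose reduction and the count restarts.
- **A single pre-cycle draw detects nothing.** That holds only if every nadir starts and ends between pre-cycle tests. The documents give no nadir timing. Carboplatin is given on day 1 only, which could produce a mid-cycle trough, but single-agent ABT-888 is taken daily.
- **The TOX suspension rule is undermined.** TOX in Section 14.3 requires a delay of more than two weeks or removal from treatment. A nadir of a few days that recovers before the next cycle does not produce that delay, and one that outlasts the cycle is seen at the pre-cycle test.
- **Footnote a and Section 6 contradict each other.** One sets how often blood is drawn and the other sets when a cycle may start. They can both be followed.

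**Conclusion.** The point holds as a matter of ascertainment in a secondary, descriptive analysis. By-course tables under Section 14.1 can combine courses with three draws and courses with one, so recorded laboratory toxicity in later courses can be lower because less blood was drawn. In such courses the recorded nadir count would be shallower and the recorded grade 3-4 rate lower.

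At constant true risk, one test records about 34-72% of the weekly-test rate, or about 67-86% at half uptake. These ranges rest on assumed per-test risks of 2-10%, correlations of 0-0.95 and an assumed uptake, so the direction is better supported than the size. The effect sits mainly in patients without a recent detected grade 3-4 ANC or platelet event. It may differ between regimens.

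The response endpoint is unaffected, as is the MTD, which Section 5.4 bases on cycle 1, before the option can apply. The TOX rule is not materially affected.

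**What to change.** Amend Section 14.1 as follows.
- Base any by-course trend, and the single-agent versus combination comparison, of laboratory nadirs and grades on cycles 1-2 of each regimen, where weekly draws are required for all patients.
- Report later courses in a separate table with the number of draws per patient-course, labelled as possibly sampled once per cycle.
- Keep worst grade over all courses in the overall safety summary, so that late toxicity such as cumulative anemia stays visible.

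Do not restrict the comparison to whichever courses happened to have weekly draws. After cycle 2, the courses that still require them belong to patients with values above grade 1 or a recent dose change, so that restriction would select on toxicity.

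The cost is a change of analysis wording and one extra table, with no new data and no change to clinical rules. The downside is that the by-course comparison rests on fewer courses and says little about trends beyond course 2.

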Adverse Events with Possible Relationship to ABT-888 (Veliparib) (CTCAE 5.0 Term) [n= 2310]			Specific Protocol Exceptions to Expedited Reporting (SPEER)
Likely (>20%)	Less Likely (<=20%)	Rare but Serious (<3%)	
	Anorexia		Anorexia (Gr 2)
	Dehydration		Dehydration (Gr 3)
	Hypophosphatemia		Hypophosphatemia (Gr 3)
NEOPLASMS BENIGN, MALIGNANT AND UNSPECIFIED (INCL CYSTS AND POLYPS)			
		Leukemia secondary to oncology chemotherapy	
		Myelodysplastic syndrome	
		Treatment related secondary malignancy	
NERVOUS SYSTEM DISORDERS			
	Dizziness		
	Dysgeusia		Dysgeusia (Gr 2)
	Headache		Headache (Gr 3)
		Seizure	
SKIN AND SUBCUTANEOUS TISSUE DISORDERS			
	Rash maculo-papular		
VASCULAR DISORDERS			
		Thromboembolic event 	

This table will be updated as the toxicity profile of the agent is revised. Updates will be distributed to all Principal Investigators at the time of revision. The current version can be obtained by contacting [[contact]](mailto:[contact]). Your name, the name of the investigator, the protocol and the agent should be included in the e-mail.

Thromboembolic events, including deep vein thrombosis and pulmonary embolism, have been observed at a higher frequency compared to control arm when administered in combination with temozolomide.

**Adverse events reported on ABT-888 (Veliparib) trials, but for which there is insufficient evidence to suggest that there was a reasonable possibility that ABT-888 (Veliparib) caused the adverse event:**

**BLOOD AND LYMPHATIC SYSTEM DISORDERS** - Bone marrow hypocellular; Blood and lymphatic system disorders - Other (pancytopenia)

**CARDIAC DISORDERS** - Cardiac disorders - Other (Takotsubo cardiomyopathy); Heart failure; Left ventricular systolic dysfunction; Palpitations; Sinus bradycardia; Sinus tachycardia

**EAR AND LABYRINTH DISORDERS** - Vertigo

**EYE DISORDERS** - Blurred vision

**GASTROINTESTINAL DISORDERS** - Abdominal distension; Ascites; Colitis; Colonic obstruction; Dental caries; Dry mouth; Duodenal ulcer; Dyspepsia; Dysphagia; Enterocolitis; Esophagitis; Flatulence; Gastritis; Gastroesophageal reflux disease; Lower gastrointestinal hemorrhage; Mucositis oral; Obstruction gastric; Rectal hemorrhage; Rectal pain; Small intestinal obstruction

**GENERAL DISORDERS AND ADMINISTRATION SITE CONDITIONS** - Chills; Edema limbs; Fever; Flu like symptoms; Malaise; Non-cardiac chest pain; Pain

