### 7.1.1. Adverse Event List for Carboplatin

Some of the expected adverse events from carboplatin are listed below. For further description of adverse events see Package Insert.

Hematologic:	Myelosuppression
Gastrointestinal:	Nausea, vomiting, diarrhea, weight loss, constipation, gastrointestinal pain
Metabolic:	Electrolyte imbalances, hypomagnesemia, hypocalcemia, hyponatremia, hyperuremia
Hepatic toxicity:	Elevated alkaline phosphatase, AST, and total bilirubin
CNS:	Peripheral neuropathies (mild paresthesias, clinical ototoxicity and other sensory abnormalities are rare)
Genitourinary:	Renal tubular damage, renal insufficiency, impotence, sterility, amenorrhea, gynecomastia
Allergy:	Anaphylactoid and urticarial reactions (acute), flushing, rash, pruritis and rarely hypotension or bronchospasm
Other:	Alopecia, pain, asthenia and mucosal side effects, decreased serum electrolytes values (sodium, magnesium, calcium and potassium)

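### Phosphorus is measured only before treatment and magnesium never, so hypophosphatemia and hypomagnesemia, both on the protocol's own toxicity lists, are ascertained incompletely

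*Combined protocol and SAP*

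**What the plan says.** The Study Calendar (Section 11) schedules serum chemistry pre-study, every week on treatment and off study. Footnote a allows a reduction to once per cycle after two cycles if the latest results show nothing above grade 1. Footnote b defines the panel: "Albumin, alkaline phosphatase, total bilirubin, bicarbonate, BUN, calcium, chloride, creatinine, glucose, potassium, total protein, SGOT [AST], SGPT [ALT], sodium". It then restricts phosphorus to the pre-study sample: "SGOT [AST], SGPT [ALT], sodium. Phosphorous at pre-study only". Magnesium does not appear. No other section schedules either test during treatment.

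The toxicity lists in Section 7.1.1 name both abnormalities:

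- **ABT-888.** The CAEPR table is headed "Adverse Events with Possible Relationship to ABT-888 (Veliparib) (CTCAE 5.0 Term) [n= 2310". It places hypophosphatemia in the column for events at up to 20% and gives it an entry in the expedited-reporting exceptions, "Hypophosphatemia (Gr 3".
- **Carboplatin.** The metabolic row reads "Electrolyte imbalances, hypomagnesemia, hypocalcemia, hyponatremia, hyperuremia", and the last row adds "decreased serum electrolytes values (sodium, magnesium, calcium and potassium".

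Section 1.2 makes the safety and tolerability of ABT-888, alone and with carboplatin, a secondary objective. Section 14.1 will summarise toxicities by type, "severity (by CTCAE and nadir or maximum values for the laboratory measures", onset, duration and reversibility, and tabulate them by course. Section 6 says that toxicities outside a short list of exceptions "should have resolved to grade 1 or lesser severity before initiation of the next cycle of therapy".

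**The concern.** A laboratory abnormality that is often silent is counted reliably only if the analyte is measured on a schedule. Here the plan names two such abnormalities and schedules no on-treatment measurement of either. The other laboratory events in the ABT-888 possible-relationship table (anemia and low lymphocyte, neutrophil, platelet and white cell counts) are all followed by the scheduled CBC. Hypophosphatemia is the only one whose test stops once treatment begins. Of the four electrolytes named in the last row of the carboplatin list, sodium, calcium and potassium are in the panel and magnesium is not.

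What is at stake is the reading of the safety tables. A low count of either event could be taken as evidence that it is uncommon with this treatment, when it may partly reflect how seldom anyone looked. The phosphorus gap affects all patients. The magnesium gap matters mainly for those given carboplatin, in the safety lead-in and after progression.

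**Working it through.** The plan states no figure to reproduce. The check compares the panel with the lists, followed by an illustration of scale.

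**Step 1. Panel against lists.**

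| Analyte | Named as a toxicity | Scheduled at baseline | Scheduled on treatment |
|---|---|---|---|
| Phosphorus | ABT-888, possible relationship (7.1.1) | Yes | No |
| Magnesium | Carboplatin, expected, named twice (7.1.1) | No | No |
| Sodium, calcium, potassium | Carboplatin, expected (7.1.1) | Yes | Yes |
| Blood counts | ABT-888, possible relationship (7.1.1) | Yes (CBC) | Yes (CBC) |

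Scheduled on-treatment measurements are 0 for phosphorus and 0 for magnesium. Magnesium also lacks a baseline, so an unscheduled low value could not be read as a change from entry.

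**Step 2. Panel against the analysis.** Nadir, onset by course, duration and reversibility each need repeated on-treatment values. Without a schedule they can be given only for patients who happened to be tested.

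**Step 3. Panel against the recovery rule.** The exceptions in Section 6 include chemistry findings such as hyperglycemia and hypoalbuminemia, so the rule reaches laboratory abnormalities. Neither phosphorus nor magnesium is exempt. The dose-limiting toxicity definition in Section 5.2 does not exclude them either.

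**Step 4. Scale, under assumed rates.** Inputs: n = 44 (Phase II maximum) and n = 20 (Phase II minimum), both from the synopsis; a ceiling of 20% from the CAEPR column. The CAEPR gives no lower bound, so q runs from an assumed 1% up to that ceiling.

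Expected patients affected = n × q. Chance of at least one = 1 − (1 − q)^n.

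| Assumed rate q | Expected, n = 44 | At least one, n = 44 | Expected, n = 20 | At least one, n = 20 |
|---|---|---|---|---|
| 1% | 44 × 0.01 = 0.4 | 1 − 0.99^44 = 36% | 20 × 0.01 = 0.2 | 1 − 0.99^20 = 18% |
| 3% | 44 × 0.03 = 1.3 | 1 − 0.97^44 = 74% | 20 × 0.03 = 0.6 | 1 − 0.97^20 = 46% |
| 10% | 44 × 0.10 = 4.4 | 1 − 0.90^44 = 99% | 20 × 0.10 = 2.0 | 1 − 0.90^20 = 88% |
| 20% | 44 × 0.20 = 8.8 | 1 − 0.80^44 > 99.9% | 20 × 0.20 = 4.0 | 1 − 0.80^20 = 99% |

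These are patients who would have hypophosphatemia, not patients who would be missed. The share that symptoms or local tests would pick up is not in the documents. No such table can be made for hypomagnesemia, because no rate is given.

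**The case against.** The case on the other side has several parts.

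- **Other routes of capture exist.** Adverse events are evaluated throughout treatment (Section 11) and all must be reported (Section 8.1). A reader might infer that the tables will show zero or near-zero rates. The documents do not support that: symptomatic cases and locally ordered tests would be recorded. What stands is that this capture is incomplete and varies by site.
- **Listing an event is not a promise to test for it.** Section 14.1 summarises toxicities that are observed, and the explicit pre-cycle laboratory values in Section 3.1.8 include neither electrolyte. So the plan does not commit to an analysis that it then makes impossible. This is a gap in ascertainment, and it stands as that.
- **The rate is uncertain at the low end.** One might read 3% as a floor, because the next CAEPR column is for events below 3%. That column is for events that are both rare and serious, so a non-serious event below 3% could sit in the column for up to 20%. Footnote 2 of the CAEPR also refers to combination use, so the table is not a single-agent rate. Both points are accepted, which is why the range starts at 1% and is only an illustration.
- **It is late.** Table 4 records that, as of 8/6/18, accrual was closed and three patients remained, all on single-agent ABT-888. Section 5.1 ends treatment by December 31, 2024. New testing can reach few patients, and on that record none receiving carboplatin. This moves the useful remedy to reporting.
- **New values are not neutral.** Grade 2 or higher results could engage Section 6 (recovery before the next cycle), Sections 6.2.3 and 6.2.5 (withholding and reduction) and the unacceptable-toxicity definition under Toxicity/Safety Monitoring. This is a real cost and has to be stated.

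**Conclusion.** The mismatch between footnote b and the protocol's own toxicity lists is real. On-treatment ascertainment of hypophosphatemia and hypomagnesemia depends on symptoms or unscheduled tests, so counts are biased downward by an amount that the documents do not allow one to calculate. If the true hypophosphatemia rate lay anywhere from 1% to 20%, between 0.4 and 8.8 of 44 patients, or 0.2 and 4 of 20, would have the event, with no scheduled test to find it.

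Two further inferences would go beyond the text. The first is that these are established drug-related toxicities: the protocol says possible relationship for ABT-888 and expected for carboplatin, and it lists hypomagnesemia among events with insufficient evidence of causation by ABT-888. The second is that the combination dose from the lead-in is undermined because its toxicity definition would have included severe electrolyte events: the documents give no rate of such events, so nothing can be concluded about it.

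The point bears on a secondary safety objective and leaves the primary response endpoint untouched. With accrual closed, most of its value lies in how the results are reported.

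**What to change.** Reconcile footnote b of Section 11 with the two adverse-event lists in Section 7.1.1, the recovery rule in Section 6 and the toxicity summary in Section 14.1.

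1. **Reporting, for all treated patients.** Describe both events as *not systematically assessed on treatment*, next to any cases captured. Where possible, give the number of patients with at least one on-treatment value. Magnesium is best reported separately for patients who received carboplatin. This costs a footnote and a data query.
2. **Collection, for any patient still on treatment.** Remove the pre-study restriction on phosphorus and run it, with magnesium where carboplatin is given, on the chemistry samples already drawn. Section 11 lets long-term single-agent patients have laboratory work done locally every three weeks, so local laboratories would need the instruction too. The cost is two analytes at most, with no added visit or draw.
3. **Interaction with existing rules.** Before adding the tests, the sponsor should state how grade 2 or higher values are handled under Sections 6, 6.2.3 and 6.2.5 and the unacceptable-toxicity definition. This point takes no position on what that handling should be.

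The safety table may look slightly less favourable once low-grade laboratory events are recorded.
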